**Additional minor changes have been made to improve clarity and consistency.**

## CLINICAL PROTOCOL SYNOPSIS

Title of Study:	A Phase 2a, randomized, double-blind, placebo-controlled study of oral FXR modulator EYP001a combined with nucleos(t)ide analogues (NA) in virologically suppressed chronic hepatitis B patients to improve functional cure rates
Protocol Number:	EYP001-201
EudraCT number	2019-001629-28
Investigational Product:	Name: EYP001a tablets Dose: 200 mg (1x tablet of 200 mg) Route of Administration: Oral
Reference/Comparator Product:	Name: Matching Placebo tablets Dose: 1 matching tablet Route of Administration: Oral
Combination Treatment:	NA: Entecavir (ETV) 0.5 mg daily (or per country specific label) or Tenofovir Disoproxil Fumarate (TDF) 300 mg daily which is equivalent to 245 mg of tenofovir disoproxil per country specific label, will be provided as the standard of care (SOC)
Indication:	Chronic hepatitis B (CHB)
Phase of Development:	Phase 2a
Study Centres:	Multi-centre study
Number of Planned Participants:	49 patients are planned to be enrolled from approximately 14 sites
Study Objectives:	
Primary Objective:
 
 
• To determine the effect of EYP001a on top of NA SOC therapy) on Hepatitis B surface antigen (HBsAg) plasma levels
 
 
Secondary Objectives:
 
 
• To establish the effect of EYP001a on top of NA on HBsAg responder rate at the end of the 16-week EYP001a treatment and at 24-week of follow-up (Week 40).
 
• To establish the effect of EYP001a on top of NA on HBsAg loss rate at the end of the 16-week EYP001a treatment and at 24-week of follow-up (Week 40).
 
• To establish the HBV virologic failure rate (breakthrough) during the 24 weeks follow-up period after stopping EYP001a with ongoing NA (SOC therapy).
 

 Breakthrough is defined by quantifiable HBV DNA increase of  $\geq 1 \log_{10}$  HBV DNA copies/mL above LLOQ. Breakthrough samples will be further assessed for resistance assessments, including both for the nucleos(t)ide analogue as well as for EYP001a (e.g., sequence analysis of FXR response elements in HBV genome). Details will be described in the Laboratory manual.

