#### 4.2. Inclusion Criteria

Patients must satisfy all of the following criteria during screening to be enrolled in the study:

1. Has given voluntary written informed consent before performance of any study related procedure.
2. Must be 18 to 65 years of age, inclusive
3. Are on stable NA therapy at least 12 months from the screening date (ETV or TDF)
4. Has virally suppressed CHB:
  - a. HBV DNA <LLOQ and serum HBsAg >100 IU/mL
5. Has liver imaging to screen for hepatocellular carcinoma or concomitant pancreaticobiliary disease either in the prior 6 months or at screening.
6. Has liver tests during the Screening Period defined as follows:
  - a. The baseline values (i.e. two measurements at least 3 days apart: one can be

---

 The performance characteristics of the quantitative HBV DNA assay will be reported in the laboratory manual. The same assay will be used for all study visits. An FDA approved test will be used such as Abbott Realtime HBV Assay or COBAS HBV Test.

 Or equivalent effective NA: Lamivudine, adefovir dipivoxil, ETV, telbivudine and TDF have been approved in most Asia Pacific countries. Patients will be switched to ETV 0.5 mg or Tenofovir Disoproxil 245 mg or Tenofovir Disoproxil Fumarate (TDF) 300 mg during screening period if they are not already taking this drug with the same dosage or equivalent.

 Genotype information will be collected from medical history, if not available best effort to assess in virologically appropriate plasma sample will be used.

 The performance characteristics of the HBsAg quantitative assay will be reported in the laboratory manual. The same assay will be used for all study visits. A validated test will be used (such as Quest Diagnostics quantitative HBsAg or DIASORIN LIAISON® XL HBsAg Quant ([REF] 310250).

Rational: HBsAg level <100 IU/mL predictive for sustained response 2 years after EOT. The role of HBsAg levels in the current management of chronic HBV infection [Höner et al, 2014].

 Cross resistance has been described between lamivudine and ETV, as well as telbivudine. In case of previous therapy with lamivudine or telbivudine and current treatment with ETV, a possible cross resistance must be documented as to be unlikely by appropriate in vitro testing (mutational analysis M204V/I, rtT184, rtS202, or rtM250), else history of previous Lamivudine therapy leads to exclusion.

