### 11.4.2. Testing strategy and power for key secondary endpoints

Multiplicity is taken into account by using a combination of a hierarchical fixed test procedure and a Hochberg procedure.

Only in case the primary endpoint is significant at 16 weeks, the key secondary endpoint “HBsAg loss rate” will be tested at the same one-sided  $\alpha$  level of 0.05, using a Hochberg procedure. This procedure goes as follows: the p-values will be ordered from small to large

$p_{(1)} \leq p_{(2)}$ . largest p-value  $p_{(2)}$  will be compared to  $\alpha=0.05$ . If significant, then both hypotheses will be rejected. If not, the smallest p-value is compared to  $\alpha/2=0.025$ . If significant, then only the hypothesis corresponding to the smallest p-value is rejected.

At 40 weeks, the key secondary endpoints HBsAg responder rate and HBsAg loss rate will be tested a one-sided  $\alpha$  level of 0.05, using a Hochberg procedure.

To calculate the power to detect a difference in HBsAg loss rate, we assumed a proportion of 0.5% in the placebo arm, and of 10% in the experimental arm. A trial including 49 patients results in a power of about 55% for this endpoint (using an un-pooled estimate of the variance), using a one-sided  $\alpha$  of 0.05.

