- HBsAg responder rate (decrease from baseline ≥ 0.5 on the \log_{10} scale) at 16 of treatment and Weeks 40 of follow up.
 - Hypothesis: H_0 : Treatment is not associated with endpoint
 H_A : Treatment is associated with endpoint
 - Time Points: Week 16 and Week40.
 - The Pearson Chi-squared test will be used to compare the differences in proportions between the treatment groups at Week 16 and Week 40. At Week 16 and Week 40, this endpoint will consider multiplicity considering multiplicity by a combination of a hierarchical fixed test procedure and a Hochberg procedure (see section 3.4 for more detail). The analysis will be based on a one-sided test at a 5% level of significance.
- HBsAg loss rate (% patients with HBsAg < Lower Limit of Quantification (LLOQ)/TND) at Week 16 of treatment and Week 40 of follow-up.
 - Hypothesis: H_0 : Treatment is not associated with endpoint
 H_A : Treatment is associated with endpoint
 - Time Points: Week 16 and Week40.
 - The Pearson Chi-squared test will be used to compare the differences in proportions between the treatment groups at Week 16, and Week 40. At Week 16 and Week 40, this endpoint will consider multiplicity by a combination of a hierarchical fixed test procedure and a Hochberg procedure (see section 3.4 for more detail). The analysis will be based on a one-sided test at a 5% level of significance.
- HBsAg loss rate (% patients with HBsAg < Lower Limit of Quantification (LLOQ)/TD) at Week 16 of treatment and Week 40 of follow-up.
 - Hypothesis: H_0 : Treatment is not associated with endpoint
 H_A : Treatment is associated with endpoint
 - Time Points: Week 16 and Week 40.

- The Pearson Chi-squared test will be used to compare the differences in proportions between the treatment groups at Week 16, and Week 40. At Week 16 and Week 40, this endpoint will consider multiplicity by a combination of a hierarchical fixed test procedure and a Hochberg procedure (see section 3.4 for more detail). The analysis will be based on a one-sided test at a 5% level of significance.

3.4 Multiple Comparisons and Multiplicity Adjustments.

For the analysis of secondary endpoints during the final analysis, multiplicity will be considered by using a combination of a hierarchical fixed test procedure and a Hochberg procedure.

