Only if the primary endpoint is significant at 16 weeks, the key secondary endpoints “HBsAg loss rate (<LLOQ/TND and <LLOQ/TD)” and “HBsAg responder rates (B and A see section 3.2)” will be tested at the same one-sided α level of 0.05, using a Hochberg procedure at Week 16. This procedure goes as follows: the p-values will be ordered from small to large $p(1) \leq p(2) \leq p(3) \leq p(4)$. The largest p-value $p(4)$ will then be compared to $\alpha=0.05$. If significant, then all hypotheses will be rejected. If not, the next largest p-value $p(3)$ is compared to $\alpha/2=0.025$. If significant, then these hypotheses corresponding to $p(1)$, $p(2)$ and $p(3)$ are rejected. If not, the next largest p-value $p(2)$ is compared to $\alpha/3=0.017$. If significant, then both hypotheses corresponding to $p(1)$ and $p(2)$ are rejected. If not, the smallest p-value is compared to $\alpha/4=0.0125$. If significant, then only the hypothesis corresponding to the smallest p-value is rejected.

At 40 weeks, the key secondary endpoints HBsAg responder rates (B and A) and HBsAg loss rate will be tested a one-sided α level of 0.05, using a Hochberg procedure.

To calculate the power to detect a difference in HBsAg loss rate, we assumed a proportion of 0.5% in the placebo arm, and of 10% in the experimental arm. A trial including 49 patients results in a power of about 55% for this endpoint (using an un-pooled estimate of the variance), using a one-sided α of 0.05.

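### SAP 3.4 puts two HBsAg-loss tests with almost no power in the same Week 16 Hochberg family as the responder rates, which costs the responder claims 11 to 20 points of power under the planned effect

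*Protocol*

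**What the plan says.** The protocol synopsis lists as a secondary objective "To establish the effect of EYP001a on top of NA on HBsAg loss rate at the end of the 16-week EYP001a treatment". SAP 3.4 makes the Week 16 key secondary tests conditional on a significant primary endpoint. The family then consists of "HBsAg loss rate (<LLOQ/TND and <LLOQ/TD" and "HBsAg responder rates (B and A see section 3.2", that is, two loss hypotheses (target not detected, target detected) and responders at ≥1.0 log10 (A) and ≥0.5 log10 (B). All four "will be tested at the same one-sided α level of 0.05, using a Hochberg procedure at Week 16". The steps are 0.05, 0.025 and 0.017, and then "If not, the smallest p-value is compared to" 0.0125. SAP 3.3 specifies a Pearson chi-square test for each, and for each states: "The analysis will be based on a one-sided test at a 5% level of significance".

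The protocol is not aligned with this. Section 11.4.2 names only the loss rate at Week 16, yet describes two ordered p-values. Section 11.3.3.2 places both responder and loss rates under the scheme at Weeks 16 and 40. On power for loss, 11.4.2 says "we assumed a proportion of 0.5% in the placebo arm, and of 10% in the experimental arm", and gives about 55% with 49 patients from an un-pooled variance. Inclusion criterion 4 requires "HBV DNA <LLOQ and serum HBsAg >100 IU/mL".

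**The concern.** In a Hochberg family, hypotheses whose p-values are nearly always large take up the lenient upper steps and push the others to the strict lower ones. If both loss tests fail, the two responder rates must both reach 0.017, or one must reach 0.0125. In a family of their own, the cut-offs would be 0.05 and 0.025. That price is reasonable if the loss tests have a real chance of success, and the stated 55% suggests that they do. If the figure does not apply to the test that will be run, the responder rates lose power and almost nothing is bought for loss. A second problem is that with no loss in either arm the Pearson statistic is 0/0, so the ordered list of four p-values cannot be formed.

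**Working it through.** **Inputs.** 37:12 allocation; Week 16 effect -1.0 log10; SD 1.08 in both arms; one-sided alpha 0.05; loss 10% against 0.5% (protocol 11.4.1, 11.4.2 and 11.5; SAP 2.4 and 2.5).

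**1. The stated 55%.** Un-pooled normal approximation:
SE = √(0.005×0.995/12 + 0.10×0.90/37) = √(0.000415 + 0.002432) = 0.0534.
Power = Φ(0.095/0.0534 − 1.645) = Φ(0.136) = 55.4%. The figure reproduces.

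**2. The planned Pearson test at the same rates.** With 0/12 on placebo:
- 7/37: pooled rate 0.143, SE = √(0.143×0.857×(1/37+1/12)) = 0.116, z = 0.189/0.116 = 1.63, p = 0.052.
- 8/37: pooled rate 0.163, SE = 0.123, z = 0.216/0.123 = 1.76, p = 0.039.

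Eight losses are needed where 37×0.10 = 3.7 are expected. Exact enumeration over both arms gives power of 2.6% at 0.05 and 0.3% at 0.025.

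**3. Cost to the responder rates.** Under the planned model the responder probabilities are:
- A: Φ(0) = 50% against Φ(−1.0/1.08) = 17.7%.
- B: Φ(0.5/1.08) = 67.8% against Φ(−0.5/1.08) = 32.2%.

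I simulated trials with normal changes, one-sided Pearson tests, loss p-values set to 1, and a one-sided t-test as stand-in for the primary gate (passed in about 86%). Power for each claim:

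| Claim | 37:12, four tests | 37:12, responders only | 19:6, four tests | 19:6, responders only |
|---|---|---|---|---|
| A (≥1.0) | 42% | 62% | 17% | 35% |
| B (≥0.5) | 52% | 66% | 24% | 40% |
| At least one | 59% | 70% | 29% | 44% |

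The 19:6 columns reflect SAP section 15, which reports enrolment suspended after about 25 randomizations. At a true effect of -0.5 (SD 1.08) the cost is about 7 to 8 points at 37:12 and 5 to 6 at 19:6.

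**4. Dependence on p = 1.** With the plan's 10% against 0.5% imposed, no loss occurs in only 0.90^37 × 0.995^12 = 1.9% of trials. The four-test powers stay at about 42/52/59%, so the convention hardly matters there.

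**5. How often the statistic is undefined if loss follows the Week 16 change model.** The LLOQ is not stated. SAP 3.2 substitutes 0.015 IU/mL (not detected) and 0.04 (detected), the latter called a midpoint. That implies a limit of 2×0.04 − 0.015 = 0.065, or 0.04²/0.015 = 0.107 on a log scale. I assume 0.04 to 0.11.
- Fall needed from 100 IU/mL: log10(100/0.11) = 2.96 to log10(100/0.04) = 3.40.
- Chance of loss on EYP001a: Φ((1−2.96)/1.08) = 3.5% to Φ((1−3.40)/1.08) = 1.3%. On placebo: 0.3% to 0.08%.
- No loss in either arm: 0.9651^37 × 0.9969^12 = 26% to 0.9868^37 × 0.9992^12 = 61%.
- From 1,000 IU/mL the chance of loss is 0.3% to 0.08%, so trials without any loss are more frequent still.

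**6. Price of testing loss last.** At 10% against 0.5%, the chance of claiming loss is 1.50% in the current family and 1.47% after the responders if loss counts are drawn independently of response. If losses are nested within responders it is about 2.00% and 1.97%.

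**The case against.** Hochberg with four equal members is a valid procedure, and this is an exploratory Phase 2a trial whose title refers to functional cure. Protocol 11.4.2 singles out loss at Week 16, so placing it last reverses an apparent clinical priority. That is a fair point about preference. It does not change the finding that the loss tests cannot deliver at these sample sizes.

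The SAP nowhere sets p = 1 for an undefined test. If such tests were dropped, the cost in those trials would be zero, and if loss is truly unreachable most of the overall cost would disappear. This stands as a limit on the claim. It does not remove the cost at the plan's own loss rates (step 4), and it confirms that a rule is missing.

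A reader might infer that loss by Week 16 is practically impossible, or that the 10% assumption contradicts the -1.0 effect. The documents do not support either. The reachability figures need an assumed LLOQ and a normal tail two SDs out, and the 10% carries no time point and follows the Week 40 sentence.

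The power cost also depends on the effect. It shrinks at -0.5, and with about 25 patients the responder rates are underpowered in either arrangement.

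**Conclusion.** The concern holds as a loss of efficiency and a missing rule; it is not an error-rate fault in the Week 16 Hochberg procedure. Sharing the family with the two loss tests costs 20 points for responder A, 14 for B and 11 for at least one. These figures assume 37:12, a true effect of -1.0 with SD 1.08, the primary gate, and loss p-values that are large or set to 1. At 19:6 the cost is about 15 to 18 points, from a low base. The firmest parts need no assumption about the LLOQ: the 55% belongs to a different test statistic from the planned one, whose power is about 3%, and the SAP does not say what happens when neither arm has a loss.

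It would be tempting to add that reordering secures a 5% family-wise error for all key secondaries. It does not. Both documents test a separate Week 40 family at 0.05 with no stated gate, so the 5% holds within Week 16 only.

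**What to change.** Amend SAP 3.4, and align protocol 11.4.2, before the Week 16 database lock and unblinding described in SAP 16.1:

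1. Test the primary endpoint.
2. If it is significant, apply Hochberg to the two responder rates (cut-offs 0.05 and 0.025).
3. Only if both are rejected, apply Hochberg to the two loss hypotheses (not detected, detected).
4. Set p = 1 for a loss test when neither arm has a loss.
5. Report loss counts with exact confidence intervals in all cases.
6. Replace the 55% with the power of the Pearson test, or label it as an un-pooled approximation.

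The cost is a wording change; no data or patients are involved. Loss could be claimed only after both responder rates, which takes under 0.1 point from its chance at the plan's own rates. Loss stays a reported secondary endpoint. The Week 40 family needs its own decision, which this change does not make.

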**LIST OF ABBREVIATIONS**

AE(s)	Adverse Event(S)
ALP	Alkaline Phosphatase
ALT	Alanine Aminotransferase
Anti-HBe	Antibody to Hepatitis B e antigen
Anti-HBs	Antibody to Hepatitis B surface antigen
AST	Aspartate Aminotransferase
AUC	Area Under the Curve
AUC last	Area Under the Curve From 0 To The Last Measurable Point
AUDIT-C	Alcohol Use Disorders Identification Test-Concise
BA	Bile Acid
BID	Twice Daily
BMI	Body Mass Index
BP	Blood Pressure
BSEP	Bile Salt Export Pump
cccDNA	Covalently Closed Circular Deoxyribonucleic Acid
CDCA	Chenodeoxycholic Acid
CFR	Code of Federal Regulations
CHB	Chronic Hepatitis B infection
C max	Maximum Plasma Concentration
CRF(s)	Case Report Form(S)
CRO	Contract Research Organization
CSR	Clinical Study Report
CTCAE	Common Terminology Criteria for Adverse Events
CYP	Cytochrome
DCA	Deoxycholic Acid
DILI	Drug-Induced Liver Injury
DNA	Deoxyribonucleic Acid
DSMC	Data Safety Monitoring Committee
EC 50	50% Of Maximal Effective Concentration
ECG	Electrocardiogram
eCRF	Electronic Case Report Form
EDC	Electronic Data Capture
EoS	End of Study
ETV	Entecavir
FDA	Food and Drug Administration
FGF19	Fibroblast Growth Factor 19
FXR	Farnesoid X Receptor
GGT	Gamma-Glutamyl Transferase
GI	Gastrointestinal
HBsAg	Hepatitis B Surface Antigen
HBcrAg	Hepatitis B core-related Antigen
HBeAg	Hepatitis B e Antigen
HBV	Hepatitis B Virus
HBV DNA	Hepatitis B Virus Deoxyribonucleic Acid
HBV pgRNA	Hepatitis B Virus pregenomic RNA
HBx	Hepatitis B Virus X protein

HCC	Hepatocellular Carcinoma
HCV	Hepatitis C Virus
HDL	High Density Lipoprotein
IB	Investigator's Brochure
ICF	Informed Consent Form
ICH-GCP	International Council for Harmonisation – Good Clinical Practice
IEC	Institutional Ethics Committee
IFN	Interferon
INR	international normalized ratio
IP	Investigational Product
IR	Immediate Release
IRB	Institutional Review Board
ITT	Intent to Treat
IWRS	Interactive Web Response System
LCA	Lithocholic Acid
LDH	Lactic Acid Dehydrogenase
LDL	Low Density Lipoprotein
LLOQ	Lower Limit of Quantification
MATE1	Multidrug and Toxin Extrusion 1
MedDRA	Medical Dictionary for Regulatory Activities
mITT	Modified Intent to Treat
mRNA	Messenger Ribonucleic Acid
MRP2	Multidrug Resistance-Associated Protein 2
MS	Metabolic Syndrome
NA	Nucleos(T)ide Analogue
NTCP	Sodium Dependent Taurocholic Co Transporting Polypeptide
OATP	Organic Anion Transporter Polypeptide
ODE	Ordinary Differential Equation
PBC	Primary Biliary Cholangitis
PD	Pharmacodynamic
PE	Polyethylene
PK	Pharmacokinetic
PT	Preferred term
PVC	Polyvinyl Chloride
PVDC	Polyvinylidene Chloride
QD	Once Daily
RNA	Ribonucleic Acid
SAE(s)	Serious Adverse Event(S)
SAP	Statistical Analysis Plan
SOC	Standard of Care
SUSAR	Suspected Unexpected Serious Adverse Reaction
TDF	Tenofovir Disoproxil Fumarate
TEAE(s)	Treatment-Emergent Adverse Events
TFV	Tenofovir
T max	Time for Maximal Concentration
TSH	Thyroid Stimulating Hormone
UDCA	Ursodeoxycholic Acid
ULN	Upper Limit of Normal
USA	United States of America

VCTE	Vibration Controlled Transient Elastography
VLDL	Very Low-Density Lipoprotein
WOCBP	Women of Childbearing Potential

## INVESTIGATORS AND STUDY ADMINISTRATIVE STRUCTURE

### Investigators

The investigators are identified in separate documents in the Trial Master File.

## 1. Introduction

### 1.1. Unmet Medical Need

ENYO Pharma is developing EYP001a, a selective, synthetic, non-bile salt, carboxylic acid agonist, or modulator, of the farnesoid X receptor (FXR), for the treatment of chronic hepatitis B (CHB) virus infections. Chronic liver diseases are major public health problems [Sanyal, 2011]. Current worldwide estimations show that 844 million people have chronic liver diseases, with a mortality rate of 2 million deaths per year. Patients with chronic hepatitis B virus (HBV) infection have increased rates of liver-related mortality due to the development of complications, including fibrosis, cirrhosis, and hepatocellular carcinoma (HCC). Therefore, there is an urgent need for improved treatment options for chronic liver diseases.

### 1.2. Background

Hepatitis B is a viral infection that causes both acute and chronic disease, with widespread geographic distribution. The primary route for transmission reported in Asia is vertical transmission from mother to new-born child, while it is contracted early in childhood in sub-Saharan Africa. In contrast, individuals in North America and Europe most commonly contract hepatitis B by sexual transmission, intravenous injection drug use, or tattoos. Among the adult population exposed to hepatitis B, fewer than 5% will develop chronic infection [Hyams, 1995]. Approximately 360 million people worldwide have evidence of CHB infection [WHO, 2014].

Although HBV infection can be efficiently prevented by vaccination, and managed with available treatments, to date there is no reliable cure for the 257 million individuals that are chronically infected worldwide with only 9% being aware of their condition [WHO, 2018]. In 2017, HBV was still the main cause for liver cirrhosis and liver cancer. Current treatments can achieve viral suppression, but long-term to lifelong therapies are needed for the majority of infected patients [Misra et al., 2009].

Available standard of care (SOC) treatments based on interferon (IFN) and nucleos(t)ide analogues (NAs) often fail to induce functional cure, defined by the off-treatment suppression of viral replication and the plasma hepatitis B surface antigen (HBsAg) loss and undetectable HBV deoxyribonucleic acid (DNA) levels [EASL, 2017]. Small molecules interfering with the viral life cycle are strongly needed for more effective and better tolerated therapies.

[figure not shown]
### 1.3. Role of FXR in HBV Infection

The FXR belongs to a family of receptors known as the nuclear hormone receptors which is highly expressed in the liver, intestine, kidney, and adrenal glands. One of the primary functions of FXR activation is to maintain bile acid (BA) homeostasis and to regulate BA biosynthesis from cholesterol, as shown in [Figure 1](#).

Activation of FXR has favourable effect on liver growth and regeneration [Ali et al., 2015]. It has been shown to prevent and resolve liver fibrosis in rodents [Fiorucci et al., 2005] and to protect against HCC [Guo et al., 2015].

In addition, FXR has been found to be an important regulator of triglyceride and glucose homeostasis and a modulator of the intestinal microbiome. FXR agonists are therefore gaining attention as potential therapeutic agents in metabolic and hepatobiliary diseases.

